- Pooled RAS: this pools data from Phase 1/2/3a/3b for ARCT-154 and placebo, respectively. It will include evaluations up to Day 92 only

Modified Intent-to-Treat (mITT) Analysis Set: Includes all participants who received all protocol-required doses of study vaccine (ARCT-154 or placebo or ChAdOx1) up to the evaluation timepoint concerned, and who have no evidence of SARS-CoV-2 infection on Day 1 or up to 7 days after the 2nd study vaccination. The mITT analysis set will be analyzed according to vaccine assigned. mITT sets are defined for the following Phases of the study:

- Phase 3b mITT
- Phase 3c mITT
- Pooled mITT: this pools data from Phases 1/2/3a/3b and will include evaluations up to Day 92 only

Per-Protocol (PP) analysis Set: Includes all eligible randomized participants who received all protocol-required doses of study vaccine (ARCT-154 or placebo or ChAdOx1) up to the evaluation timepoint concerned and within the protocol predefined window, and who have no major protocol deviations expected to affect efficacy, immunogenicity, safety or reactogenicity assessments as determined by the Sponsor Medical Monitor or designee in a blinded manner. The PP analysis set will be analyzed according to which study vaccine was received, in the event there is a discrepancy. PP analysis sets are defined for the following Phases of the study:

- Phase 1 PP set: this excludes any participant that has evidence of SARS-CoV-2 infection at baseline or prior to the analysis time point concerned (IcEv3) or that receives an off-study COVID-19 vaccine prior to the analysis time point concerned (IcEv2).
- Phase 2/3a PP set: this pools data from Phase 2 and Phase 3a participants and excludes any participant that has evidence of SARS-CoV-2 infection at baseline or prior to the analysis time point concerned (IcEv3) or that receives an off-study COVID-19 vaccine prior to the analysis time point concerned (IcEv2).
- Phase 1/2/3a PP set: this pools data from Phase 1, 2 and Phase 3a participants and excludes any participant that has evidence of SARS-CoV-2 infection at baseline

or prior to the analysis time point concerned (IcEv3) or that receives an off-study COVID-19 vaccine prior to the analysis time point concerned (IcEv2). This set will include evaluations of immunogenicity up to Day 92 only.

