- Phase 3b PP set: this excludes any participant with evidence of SARS-CoV-2 infection on Day 1 or up to 7 days after the 2nd study vaccination (IcEv3) or that receives an off-study COVID-19 vaccine prior to Day 92 (IcEv2)
- Phase 3c-1 PP set: this includes just the participants enrolled in the Phase 3c-1 subset of Phase 3c but excludes any participant that has evidence of SARS-CoV-2 infection at baseline or prior to the analysis time point concerned (IcEv3) or that receives an off-study COVID-19 vaccine prior to the analysis time point concerned (IcEv2).
- Phase 3c PP set: this includes all of Phase 3c but excludes any participant that has evidence of SARS-CoV-2 infection at baseline or prior to the analysis time point concerned (IcEv3) or that receives an off-study COVID-19 vaccine prior to the analysis time point concerned (IcEv2).
- Pooled PP set: this pools data from Phase 1/2/3a/3b and excludes any participant with evidence of SARS-CoV-2 infection on Day 1 or up to 7 days after the 2nd study vaccination (IcEv3) or that receives an off-study COVID-19 vaccine prior to Day 92 (IcEv2). This will include evaluations up to Day 92 only.

Immunogenicity Analysis Set (IAS): Includes all participants who received all protocol-required doses of study vaccine (ARCT-154 or placebo or ChAdOx1) up to the evaluation timepoint concerned, who have no evidence of prior SARS-CoV-2 infection at Day 1 (IcEv3; Section 8.3.1) and who have at least 1 valid post-vaccination immunogenicity assay result. Data at timepoints following evidence of a SARSCoV2 infection (IcEv3), use of immune-modifying drugs, blood products or immunoglobulins (IcEv5) or non-study COVID-19 vaccines (IcEv2), or protocol deviations (eg, time windows for doses and blood draws for the time period summarized) that may impact immunogenicity as determined by the Sponsor Medical Monitor or designee in a blinded manner will be excluded. All participants in the IAS will be analyzed according to which study vaccine was received. IAS are defined for the following Phases of the study:

- Phase 1 IAS
- Phase 2/3a IAS: this pools data from participants in Phase 2 and 3a
- Phase 1/2/3a IAS: this pools data from Phase 1, 2 and 3a participants and will include evaluations of immunogenicity up to Day 92 only
- Phase 3b IAS
- Phase 3c-1 IAS

8.3 Statistical Considerations for Phase 3

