- **Per-Protocol (PP) analysis Set:** Includes all eligible randomized participants who received all protocol-required doses of study vaccine (ARCT-154 or placebo) up to the evaluation timepoint concerned and within the protocol predefined window, and who have no major protocol deviations expected to affect efficacy (PP efficacy), immunogenicity (PP immunogenicity), safety or reactogenicity assessments as determined by the Sponsor Medical Monitor or designee in a blinded manner. The PP analysis set will be analyzed according to which study vaccine was assigned, in the event there is a discrepancy. PP sets will be further derived for efficacy and immunogenicity as follows:
  - **Efficacy**
    - Phase 3b PP efficacy set: includes per protocol Phase 1 participants and excludes any participant with evidence of SARS-CoV-infection on Day 1 up to 7 days after the 2nd study vaccination (IcEv3) or that receives an non-study COVID-19 vaccine prior to Day 92 (IcEv2).
    - Pooled PP efficacy set: includes per protocol Phase 1, 2, 3a and Phase 3b participants and excludes any participant with evidence of SARS-CoV-infection on Day 1 up to 7 days after the 2nd study vaccination (IcEv3) or that receives an non-study COVID-19 vaccine prior to Day 92 (IcEv2).
  - **Immunogenicity**
    - Phase 1 PP immunogenicity set: includes per protocol Phase 1 participants and excludes any participant with evidence of SARS-CoV-2 infection on Day 1 up to Day 57 (IcEv3) or who receives a non-study COVID-19 vaccine prior to the analysis time point concerned (IcEv2).
    - Phase 2/3a PP immunogenicity set: includes per protocol Phase 2 and Phase 3a participants and excludes any participant with evidence of SARS-CoV-2 infection on Day 1 up to Day 57 (IcEv3) or who receives a

non-study COVID-19 vaccine prior to the analysis time point concerned (IcEv2).

- Phase 1/2/3a PP immunogenicity set (or Phase 1/2 PP immunogenicity set): includes per protocol participants from Phase 1, 2 and Phase 3a participants and excludes any participant with evidence of SARS-CoV-2 infection on Day 1 up to Day 57 (IcEv3) or who receives an non-study COVID-19 vaccine prior to the analysis time point concerned (IcEv2). This set will include evaluations of immunogenicity up to Day 92 only. Of note, this analysis set will be restricted to Phase 1/2 participants for analysis of parameters not collected in phase 3a participants and will be referred to as Phase 1/2 PP immunogenicity set)

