PP immunogenicity sets will be derived up to the analysis time point concerned based on the availability of each assay. Three time points are considered:

- Up to Day 57
- Up to Day 92
- Up to Day 120

The following major protocol deviations are expected to affect efficacy and will lead to exclusion of a participant from the PP efficacy set:

- Received wrong study vaccine up to Day 92
- Did not receive study vaccine
- Received non-study COVID-19 vaccine (IcEv2) up to Day 92
- COVID-19 infection (positive RT-PCR or other COVID-19 test) up to Day 36
- Result of SARS-CoV-2 anti-nucleocapsid antibodies test is Positive/Undetermined up to Day 36

The following major protocol deviations are expected to affect immunogenicity and will lead to exclusion of a participant from the PP immunogenicity sets:

- Received wrong study vaccine up to the time point concerned
- Did not receive study vaccine
- Received non-study COVID-19 vaccine (IcEv2) up to the time point concerned
- Received confounding medication (IcEv5) up to the time point concerned
- COVID-19 infection (positive RT-PCR or other COVID-19 test) up to Day 57
- Result of SARS-CoV-2 anti-nucleocapsid antibodies test is Positive/Undetermined up to Day 57

All major protocol deviations listed above are conditions leading to exclusion from the PP set specified in the protocol.

- **Immunogenicity Analysis Set (IAS):** Includes all participants who received all protocol-required doses of study vaccine (ARCT-154 or placebo) up to the evaluation timepoint concerned, who have no evidence of prior SARS-CoV-2 infection (no positive RT-PCR or other COVID-19 test or seropositivity for anti-nucleocapsid antibody) up to Day 57 and who have at least 1 valid post-vaccination immunogenicity assay result.

All participants in the IAS will be analyzed according to which study vaccine was assigned.

IAS are defined for the following Phases of the study:

- Phase 1 IAS: this corresponds to data from participants in Phase 1
- Phase 2/3a IAS: this pools data from participants in Phase 2 and 3a
- Phase 1/2/3a IAS (or phase 1/2 IAS): this pools data from Phase 1, 2 and 3a participants and will include evaluations of immunogenicity up to Day 92 only. Of note, this analysis set may be restricted to Phase 1 and Phase 2 participants for analyses on parameters not collected for phase 3a participants.

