### 9.2.1 Estimands for Phase 1/2/3a Substudy and Phase 3c Substudy Primary, Secondary and Exploratory Immunogenicity Endpoints

Estimand Label	Estimand 1 (immunogenicity)
Estimand Description	NAb by surrogate virus neutralization test (primary) and NAb by PRNT50 and BAb (secondary) responses at defined time points following vaccination (as defined in Section 1.2) with ARCT-154 or placebo. The primary endpoint will be measured based on responses at Day 57.
Target Population	Vaccinated participants (as defined by eligibility criteria) in Phases 1, 2 and 3a. The population includes participants without evidence of COVID-19, SARS-CoV-2 infection, or nucleocapsid antibody positivity on or prior to Day 57.
Endpoint	NAb and BAb responses as defined in Section 1.2
Treatment conditions	ARCT-154 dose 5 µg or placebo administered on Day 1 and Day 29.
Population-level Summary	

Geometric mean concentrations for NAb and BAb

The geometric mean ratio (ARCT-154 /Placebo) for NAb and BAb concentrations

Proportion of participants in each study vaccine group that demonstrate seroconversion (as defined by 4-fold increase in antibody concentration [based on international units, if available] from baseline).

Geometric mean fold rise (GMFR) for NAb and BAb

Intercurrent events (IcEv) Strategy	
IcEv1 (Death)	Treatment policy strategy
IcEv2 (Non-Study vaccine)	While on treatment strategy
IcEv3 (Early infection)	Principal stratum strategy
IcEv4 (Study infection)	Principal stratum strategy
IcEv5 (confounding on-Study Medications)	While on treatment strategy
Rationale for strategies	IcEv2 and IcEv5 could be potentially confounding to the analysis of the endpoint and result in censoring of the participant for all endpoint assessments after the time of the IcEv (while on treatment). IcEv4 and IcEv3 could also be potentially confounding but it is more difficult to determine the

	precise timing of these events, so a principal stratum strategy is used to exclude these participants from immunogenicity analyses.
--	---

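### SAP 4.1 stops the PP infection exclusion at Day 57, so Day 92 and Day 120 titres after a later infection count as vaccine or placebo response, also in the sensitivity analysis

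*SAP*

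**What the plan says.** **PP sets, SAP 4.1.** The sets move with the visit: "PP immunogenicity sets will be derived up to the analysis time point concerned based on the availability of each assay", with Day 57, Day 92 and Day 120 named. In the exclusion list, wrong study vaccine, non-study vaccine and confounding medication run to the time point in question. Infection does not: "COVID-19 infection (positive RT-PCR or other COVID-19 test) up to Day 57". A positive or undetermined anti-nucleocapsid result also stops at Day 57. Each of the three set definitions agrees: "excludes any participant with evidence of SARS-CoV-2 infection on Day 1 up to Day 57 (IcEv3"). The list closes with "All major protocol deviations listed above are conditions leading to exclusion from the PP set specified in the protocol".

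**PP sets elsewhere.** Protocol 8.2, for the Phase 1, Phase 2/3a and Phase 1/2/3a PP sets: "excludes any participant that has evidence of SARS-CoV-2 infection at baseline or prior to the analysis time point concerned (IcEv3"). The planned-analysis column of SAP 7.1 gives the same moving cut-off for the Phase 1/2/3a PP immunogenicity set.

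**IAS.** SAP 4.1 admits participants "who have no evidence of prior SARS-CoV-2 infection (no positive RT-PCR or other COVID-19 test or seropositivity for anti-nucleocapsid antibody) up to Day 57". The protocol IAS has a further sentence under which "Data at timepoints following evidence of a SARSCoV2 infection (IcEv3") are excluded; the SAP does not carry it over.

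**Data rules and estimand.** SAP 6.5 removes data after switchover or further vaccine (two-dose sets), non-study vaccine and confounding medication. It refers to SAP 9.2.1 for the handling of intercurrent events. There, IcEv3 and IcEv4 are hard to date, "so a principal stratum strategy is used to exclude these participants from immunogenicity analyses". SAP Table 5 starts IcEv4 at Day 36 and gives it no upper limit.

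**The concern.** A participant infected on, say, Day 70 stays in both the IAS and the PP set at Day 92, and the titre after that infection is summarised as a response to ARCT-154 or to placebo.

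At Day 92 this can raise the GMC and the seroconversion rate in both arms. If the vaccine works, more placebo participants are infected, so the ARCT-154/placebo ratio falls. In the three-dose analysis no between-arm ratio is planned. The Day 92 to Day 120 fold rise can move either way: an infection before Day 92 raises the reference value, and a later one raises the result.

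The PP analysis is the planned sensitivity analysis. Because it uses the same cut-off as the IAS, it cannot show the effect. The results concerned are Day 92 sVNT and binding antibody (secondary) and the Day 120 third-dose results, including variant MNT (exploratory).

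**Working it through.** **Texts side by side**

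| Source | Infection cut-off |
|---|---|
| Protocol 8.2, PP sets | moves with the time point |
| SAP 7.1, PP row | moves with the time point |
| SAP 4.1, PP sets and list | Day 57, fixed |
| SAP 4.1 and SAP 7.1, IAS | Day 57, fixed |
| SAP 9.2.1, target population | Day 57 |
| SAP 9.2.1, IcEv4 strategy with SAP Table 5 | from Day 36, no end |
| Protocol Tables 14, 15 and 18 | Day 57 |

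SAP 6.5 runs the analyses on the sets as defined in SAP 4.1, so Day 57 is what would be programmed. No row of SAP Section 7 records a change of the PP cut-off to Day 57: the PP row of 7.1 states the moving one, and 7.2 says only that the PP immunogenicity set is further defined. The labels also differ, since SAP 4.1 calls infection to Day 57 IcEv3 while SAP Table 5 ends IcEv3 at Day 35.

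**Size.** The plan gives no infection rate after Day 57 for Phase 1/2/3a and no figure on this point to reproduce. What follows is an illustration.

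Inputs: 372 cases, about 16,000 participants and 50% VE (Protocol 8.5.2, Phase 3b); arms of 750 and 250 less 10% (Protocol 8.5.1), giving 675 and 225. Assumed: a constant hazard over Day 36 to Day 92, and a fold rise k of 4 to 30 in those infected.

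1. Windows: Day 36-92 is 57 days and Day 58-92 is 35 days.
2. Share infected: f = 372/16,000 × 35/57 = 0.02325 × 0.614 = 0.0143.
3. GMC factor k^f: 1.020 (k = 4), 1.033 (k = 10), 1.050 (k = 30). With f doubled: 1.040, 1.068, 1.102.
4. By arm, with 50% VE and 1:1 allocation: placebo f_p = f/0.75 = 0.0190; ARCT-154 f_v = 0.0095. That is 225 × 0.0190 = 4.3 and 675 × 0.0095 = 6.4 participants.
5. Day 92 ratio factor k_v^f_v / k_p^f_p:

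| k_p, k_v | Base rate | Doubled rate |
|---|---|---|
| 4, 4 | 0.987 | 0.974 |
| 10, 10 | 0.978 | 0.957 |
| 30, 4 | 0.950 | 0.902 |

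6. Placebo seroconversion at Day 92: at most about 1.9 percentage points higher at the base rate, if every infected placebo participant newly seroconverts.
7. For Day 120 the window is 63 days, 63/35 = 1.8 times as long. If the same rate continued, f would be 1.8 × 0.0143 = 0.026, inside the doubled case (0.029).

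The 6000 IU/mL upper limit for the NIHE sVNT (SAP 5.2) caps any rise in that assay.

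**The case against.** The strongest reply is that Day 57 comes from the protocol itself. The protocol PP sentence carries the IcEv3 label, and the note in Protocol Table 14 makes Day 57 the dividing day for early infection in immunogenicity endpoints. Table 15 defines the target population to Day 57. Table 18 excludes infection before Day 57 and then asks for the same analysis in the PP sets. On that reading SAP 4.1 follows the protocol.

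This stands for the IAS, where SAP 7.1 records the Day 57 change and cites Tables 14 and 15. For the PP sets it makes the protocol ambiguous but does not settle the matter: the explicit PP definitions, and the SAP's own 7.1 row, say the analysis time point.

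A reader might also infer that the SAP has no rule at all for infections after Day 57. It does not go that far. SAP 6.5 points to SAP 9.2.1, whose heading covers primary, secondary and exploratory endpoints and whose IcEv4 strategy excludes these participants. The strategy is stated; the set definitions and data exclusions do not carry it out.

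Finally, the effect may be small, the illustration borrows a Phase 3b design figure, and SAP authors had access to unblinded data (SAP 2.4). All of that is true. It limits the weight of the point and argues for labelling the change, but it does not remove the contradiction.

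**Conclusion.** The point holds for the PP immunogenicity sets: SAP 4.1 contradicts the PP definitions in Protocol 8.2 and the PP row of SAP 7.1, and its statement that the list is as specified in the protocol needs correcting or explaining. For the IAS the defect is narrower. The Day 57 cut-off is supported, but the IcEv4 exclusion is not implemented after Day 57 and the protocol sentence on data after infection was not carried over.

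The size is unknown. Under the stated assumptions the Day 92 GMC is 2-5% higher and the ratio about 1-5% lower; at a doubled rate, 4-10% higher and about 3-10% lower. These figures rest on a rate from another cohort, a constant hazard and assumed fold rises.

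It would be wrong to conclude that the primary result is at risk. At Day 57 the fixed and moving cut-offs coincide, and no p-value or decision rule depends on Day 92 or Day 120. Nor do the documents show when or why the PP cut-off was set at Day 57, so nothing should be inferred about a data-driven choice. This should be corrected before the final derivations are run, but it does not threaten the trial's main conclusions.

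**What to change.** 1. In SAP 4.1, run the PP infection and anti-nucleocapsid exclusions to the analysis time point for Day 92 and Day 120, as in Protocol 8.2 and SAP 7.1. Keep Day 57 for the Day 57 analysis. Correct the statement that the list matches the protocol, and label the change as made after unblinding.
2. Keep the Day 57 IAS. Add a supplementary Day 92 and Day 120 analysis, labelled as specified after unblinding, that drops a participant's data from the first time point after an infection, alongside the existing rules for non-study vaccine and confounding medication.
3. Align SAP 4.1, 7.1, 9.2.1 and Table 5, including the day on which IcEv3 ends. Record the changes in Section 7, with the omitted protocol IAS sentence.

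**Cost.** SAP wording and one derivation; SAP 4.2 already has the PP exclusions re-programmed on the locked data. Results to Day 120 were presented at the 6-month analysis (SAP 2.5), hence the labels. The Day 92 and Day 120 sets become slightly smaller and differ from the Day 57 set, with proportionally more placebo participants removed if the vaccine works. This selection on a post-randomisation event is already the SAP's stated strategy, but should be acknowledged.

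**Feasibility.** Protocol 4.5.5.3 schedules anti-nucleocapsid draws at Day 92 (Phase 1/2/3a) and Day 120 (Phase 2/3a). SAP 9.3 lists nucleocapsid only in the MSD assay at Day 1 and Day 57, so confirm that the later results exist. Swabs are not required after Day 92 in these phases, so detection after that day will be incomplete.

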## 4.2 Protocol Deviations

A deviation from the protocol is an unintended or unanticipated departure from the procedures or processes approved by the Sponsor and the IRB/IEC and agreed to by the investigator. A significant deviation occurs when there is non adherence to the protocol or to local regulations or ICH GCP guidelines that may or may not result in a significant, additional risk to the participant or impacts the integrity of study data.

The process for determining which deviations would result in participants being removed from the PP analysis set for immunogenicity is described in Section 4.1. Derivations for exclusion from PP analysis set will be re-programmed for the final analysis using the final locked data from EDC.

A summary of major protocol deviations, and the reasons for exclusion from efficacy and immunogenicity analyses will be presented by treatment group in the Randomized Set, and detailed data will be provided in the listing.

## 5 DATA HANDLING

### 5.1 Computing Environment

All statistical analyses will be performed using SAS statistical software (Version 9.4), unless otherwise noted. Medical History and adverse events will be coded using Medical Dictionary for Regulatory Activities (MedDRA) version 24.0. Concomitant medications will be coded using World Health Organization (WHO) Drug Dictionary version March 2022.

### 5.2 Data Conventions

- **Day 1:** The date of first dose of study vaccine administration
- **Day 92:** refers to Day 92 visit unless otherwise specified in efficacy Section 6.4
- **Unscheduled or repeated visits:** Unscheduled visits results will be listed, but not included in tables or graphs.
- 1 year = 365.25 days
- **Values below the lower limit of quantification (LLOQ):** Any immunogenicity parameters which are below LLOQ will be listed, and LLOQ/2 will be used for summaries. Additional analyses of seroconversion with a different imputation of LLOQ value will be performed as previously requested by US FDA.
- **Values above the upper limit of quantification (ULOQ):** Any immunogenicity parameters which are above ULOQ will be listed, for summaries ULOQ will be used. For Neutralizing antibody (NAb) responses by surrogate virus neutralization test (sVNT) as performed by National Institute of Hygiene and Epidemiology, Department of Virology, Vietnam (NIHE), ULOQ will be 6000 IU/mL.
- (Absolute) Change from baseline = Value at the time point – Baseline value, or specified otherwise.

### 5.3 Reporting of data across studies and Output Displays

The data collected in phase 1, phase 3b and phase 3c will be reported separately as applicable. In addition, the following pooling will be performed as applicable:

- Phase 2/3a; Phase 2 and 3a will be pooled together, where data are available for each of the phases
- Phase 1/2/3a: Phase 1, 2 and 3a will be pooled together, where data are available for each of the phases
- Pooled: Phase 1, 2, 3a, 3b will be pooled together, where data are available for each of the phases

### 5.3.1 Output Displays

#### Phase 1 and Phase 3b:

- Baseline and disposition outputs:

ARCT-154 (Initial)	Placebo (Initial)	Total
--------------------	-------------------	-------

- Analysis of data up to the Switchover/Further study vaccine or after any dose:

ARCT-154 (Initial)	Placebo (Initial)
--------------------	-------------------

- Analysis of data after Switchover/Further study vaccine

ARCT-154 (Initial)/ Placebo (Dose 3 and 4)	Placebo (Initial)/ ARCT-154 (Dose 3 and 4)
---	---

